9.1.3 Serious Adverse Events (SAE)

A serious adverse event (SAE) based on ICH and EU Guidelines on Pharmacovigilance for Medicinal Products for Human Use is any untoward medical occurrence that at any dose:

- Results in death.
- Is life-threatening (i.e., immediate risk of death from the reaction as it occurred).
- Requires or prolongs inpatient hospitalization (i.e., the event required at least a 24-hour hospitalization or prolonged a hospitalization beyond the expected length of stay). Hospitalization admissions and/or surgical operations scheduled to occur during the study period, but planned prior to study entry are not considered SAEs if the illness or disease existed before the person was enrolled in the trial, provided that it did not deteriorate in an unexpected manner during the trial (e.g., surgery performed earlier than planned)
- Results in persistent or significant disability/incapacity. Disability is defined as a substantial disruption of a person's ability to conduct normal life functions
- Results in a congenital anomaly or birth defect
- Is a suspected transmission of any infectious agent via a medicinal product
- Is an important medical event when, based upon appropriate medical judgment, it may jeopardize the participant and require medical or surgical intervention to prevent one of the outcomes listed above. Examples of such medical events include allergic bronchospasm requiring intensive treatment in an emergency room or at home; blood dyscrasias or convulsions that do not result in inpatient hospitalization, or the development of drug dependency or drug abuse

Events **not** considered to be SAEs are hospitalizations for:

- Routine treatment or monitoring of the studied indication, not associated with any deterioration in condition
- Elective or pre-planned treatment for a pre-existing condition that did not worsen
- Emergency outpatient treatment for an event not fulfilling the serious criteria outlined above and not resulting in inpatient admission
- Respite care or social admissions

9.1.4 Expectedness

An adverse event or suspected adverse reaction is considered “unexpected” if it is not listed in the Investigator’s Brochure or is not listed at the specificity or severity that has been observed.

Unexpected, as used in this definition, also refers to adverse events or suspected adverse reactions that are mentioned in the Investigator’s Brochure as occurring with a class of

drugs or as anticipated from the pharmacological properties of the drug, but are not specifically mentioned as occurring with the particular drug under investigation. Such events would be considered unexpected until they have been observed with the drug under investigation.

9.1.5 Attribution

A suspected adverse reaction means any adverse event for which there is reasonable possibility that the study drug caused the adverse event. For the purposes of IND safety reporting, “reasonable possibility” means there is evidence to suggest a causal relationship between the drug and the adverse event.

The Investigator will assign attribution of the possible association of the event with the study drug using the following definitions:

- **Unrelated to study drug:** The adverse event is *clearly not related* or is *doubtfully related* to the study drug
- **Related to study drug:** The adverse event *may be related*, is *likely related*, or is *clearly related* to the study drug

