5.3.5 Dose Modifications

Intra-patient dose interruptions and/or reductions will be permitted provided that study discontinuation criteria have not been met (please see Section 10).

- Patients experiencing treatment-related seizure of any grade will have study drug permanently discontinued.
- For patients experiencing Grades 1-2 treatment-related adverse events, short treatment breaks can be instituted as per the discretion of the Investigator until the severity of the toxicity decreases to Grade 1 or returns to baseline. If toxicity recurs, dose reductions to the next lower dose level will be allowed as per the discretion of the Investigator.
- For patients experiencing Grade 3 treatment-related adverse events other than seizure, study drug should be held. If the severity of the toxicity decreases to Grade 1 or returns to baseline within two weeks, study treatment may be resumed at the next lower dose level, except for clinically insignificant laboratory abnormalities that resolve within two days on optimal treatment, in which case dose reduction is not required. If toxicity recurs at Grade 3 or higher, the dose of apalutamide should be reduced to the next lower dose level. A maximum of 2 dose level reductions will be allowed (Table 1).
- For patients experiencing Grade 4 treatment-related adverse events, except for clinically insignificant laboratory abnormalities that resolve within two days on optimal treatment, study treatment must be permanently discontinued.
- Any patient requiring > 14 days delay in treatment due to study treatment-related AEs should discontinue treatment of the study treatment thought to be responsible for the AE.

Table 1 Apalutamide Dose Levels

Dose Level	Total Daily Dose	Number of 60-mg Tablets (QD)
0	240 mg	4
-1	180 mg	3
-2	120 mg	2

Doses reduced for study treatment-related toxicities should generally not be re-escalated, however, re-escalation back to the previous dose level may be permitted at the discretion of the Principal Investigator.

Rash

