12.2.2 Analyses of Secondary Endpoints

Comparison of time to PSA progression will be performed using a two-sided log-rank test. Kaplan-Meier methods will be used to estimate medians for each treatment arm. Cox proportional-hazard models, including the same factors as above, will be used to estimate the hazard ratio and its 95% confidence interval (CI).

Adverse events (AEs) will be graded according to the NCI Common Terminology Criteria for Adverse Events (CTCAE) Version 4.03. All AEs reported from the first dose of study drug until 30 days after the last dose of study drug will be considered as treatment-emergent AEs and will be summarized by treatment arm. For each treatment arm, adverse event incidence rates will be summarized with frequency and percentage, with all patients treated in that treatment arm as the denominator, unless otherwise specified. In addition, AE incidence rates will also be summarized by severity and relationship to study drug. Treatment-related AEs are those judged by the Investigator to be at least possibly related to the study treatment. Adverse events with missing severity or relationship to study drug will be classified as severe and treatment-related, respectively.

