3.1 Adverse Event Monitoring

All Grade 3-5 adverse events (AEs), regardless of being unexpected or considered to be associated with the use of the study drug will be entered into OnCore®, UCSF's Clinical Trial Management System.

Adverse events are graded according to the Common Terminology Criteria for Adverse Events (CTCAE) as developed and revised by the Common Therapy Evaluation Program (CTEP) of the National Cancer Institute. Adverse events are further given an assignment of attribution or relationship to the investigational agent(s) or study procedure. Attribution categories are:

- Definite – The adverse event is clearly related to the investigational agent(s) or study procedure.
- Probable – The adverse event is likely related to the investigational agent(s) or study procedure.
- Possible – The adverse event may be related to the investigational agent(s) or study procedure.
- Unrelated – the adverse event is clearly not related to the investigational agent(s) or study procedure.

All Grade 3-5 adverse events entered into OnCore® will be reviewed on a monthly basis at the UCSF Site Committee meetings. All adverse events entered into OnCore® will be reviewed on a monthly basis at the UCSF Coordinating Center Site Committee meetings. All grade 3-5 adverse events must be reported to the UCSF Coordinating Center by the participating sites within 10 business days of becoming aware of the event or during the next scheduled monthly conference call, whichever is sooner. The UCSF Site Committee will review and discuss the selected toxicity, the toxicity grade, and attribution assignment from the UCSF Coordinating Center and the participating sites.

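### No required field attributes adverse events to SBRT, so events caused by SBRT alone are coded unrelated and drop out of the summary by relationship to study drug

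*Combined protocol and SAP*

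**What the plan says.** Section 9.1.5 sets the attribution rule: "The Investigator will assign attribution of the possible association of the event with the study drug using the following definitions". It has two categories. Unrelated covers events that are clearly not or doubtfully related to the drug; Related covers those that may be, are likely or are clearly related. The same section defines a suspected adverse reaction by the drug alone: "A suspected adverse reaction means any adverse event for which there is reasonable possibility that the study drug caused the adverse event". Section 9.2 has the Site Committee review attribution to the study drug(s). Section 9.3.1 requires the case report form to carry the investigator's opinion on relationship to the manufacturer's product.

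Appendix 6, Section 3.1, uses another scale (Definite, Probable, Possible, Unrelated) and another target: "Adverse events are further given an assignment of attribution or relationship to the investigational agent(s) or study procedure".

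For the analysis, Section 12.2.2 says that "AE incidence rates will also be summarized by severity and relationship to study drug". It then says: "Treatment-related AEs are those judged by the Investigator to be at least possibly related to the study treatment". It also counts an event whose relationship to study drug is missing as treatment-related. Separately, it summarises all treatment-emergent events by arm, with all patients treated in that arm as the denominator.

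**The concern.** Both arms receive apalutamide, so the safety question peculiar to this trial is what SBRT adds. Sections 2.2 and 3.2.2 make the safety of the combination a secondary objective and endpoint. A reader will expect a table of events related to SBRT, or at least a table of treatment-related events that includes them. If the only mandated judgement concerns the drug, the first table cannot be built from required data. The second depends on whether the programmer reads Section 12.2.2 as meaning study drug or study treatment. On the drug reading, toxicity from the experimental component appears under unrelated.

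**Working it through.** The plan states no figure on this point, so there is none to reproduce. The check sets the attribution rules side by side, traces one event through them, and then asks how far the by-arm table makes up for the gap.

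**1. The rules side by side**

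| Place | Judged against | Scale |
|---|---|---|
| 9.1.5 | study drug | two levels; doubtful counted as unrelated |
| 9.2 | study drug(s) | none given |
| 9.3.1 | manufacturer's product | none given |
| 12.2.2, summary | study drug | none given |
| 12.2.2, definition | study treatment | cut at possibly related |
| Appendix 6, 3.1 | agent(s) or procedure, one judgement | four levels; no doubtful level |

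No row asks for a judgement about SBRT by itself.

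**2. One event traced through.** Take an injury in Arm B that the investigator attributes to SBRT and not to apalutamide.

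- Under 9.1.5 it is unrelated to study drug. That is the correct coding.
- In the 12.2.2 summary by relationship to study drug it falls in the unrelated part.
- Under the 12.2.2 definition it should count as treatment-related. SBRT is a study treatment: Section 5 on study treatments contains 5.6 on SBRT, and Section 3.1 describes early SBRT as part of study treatment. But the mandated drug field reads unrelated, and no other mandated field can bring the event in.
- The missing-data rule in 12.2.2 treats the two terms as interchangeable. An event with a blank drug field counts as treatment-related, while the correctly coded SBRT injury does not.
- Under Appendix 6 the event is related if SBRT is a study procedure, which is never stated. It then cannot be told apart from an apalutamide event. If SBRT is not a study procedure, the event is missed there too.

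**3. The two scales.** Three levels correspond closely. For example, the Possible level in Appendix 6 ("The adverse event may be related to the investigational agent(s) or study procedure") matches the lowest Related level in 9.1.5, and that is also the cut-point in 12.2.2. The exception is the doubtful category. Section 9.1.5 puts it under unrelated, whereas the Appendix 6 Unrelated level requires that "the adverse event is clearly not related to the investigational agent(s) or study procedure". The scales therefore differ in one category and in the target.

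**4. What the by-arm table recovers.** All treatment-emergent events are counted whatever their attribution, so the difference between arms in all-cause rates estimates the added toxicity. Its 95% half-width with 30 per arm (Section 3.1.1) is

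1.96 × √[pA(1 − pA)/30 + pB(1 − pB)/30].

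The documents give no event rates for this combination, so the rates below are assumptions.

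- 5% v 20%: 1.96 × √(0.00158 + 0.00533) = 0.163, so 15 ± 16 points
- 10% v 20%: 1.96 × √(0.00300 + 0.00533) = 0.179, so 10 ± 18 points
- 10% v 30%: 1.96 × √(0.00300 + 0.00700) = 0.196, so 20 ± 20 points

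Over a wider set of assumed pairs, from 5% v 10% to 10% v 40%, the half-width runs from 13 to 21 points. Section 12.2.2 plans no test of adverse events. For scale only, a two-sided 5% Fisher's exact test would have 24%, 10% and 37% power in the three cases listed.

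**The case against.** The strongest reply is that the main safety comparison does not depend on attribution. Both arms receive apalutamide, allocation is randomised, and every treatment-emergent event is tabulated by arm. Timing helps as well. SBRT must start within 90 days, and the reporting window for a man who completes 52 weeks runs to day 364 + 30 = 394, so at least 394 − 90 = 304 days follow the start of SBRT. This stands. A reader might infer that SBRT toxicity is lost, or can never be separated from drug toxicity. The documents do not support that at arm level. Serious events also reach the monitoring committee whatever their attribution, and the rule for notifying related deaths covers study procedures.

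Second, drug-specific attribution in 9.1.5 suits IND and manufacturer reporting. This also stands: that judgement should be kept, and the gap is that nothing sits beside it for SBRT.

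Third, a reader might infer that the two scales are incompatible. They are not; only the doubtful category and the target differ.

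Fourth, Section 5.3.5 (a patient with a long treatment delay "should discontinue treatment of the study treatment thought to be responsible for the AE") and Section 4.3 (events related to either component) might seem to prove that the protocol contradicts itself. They do not. They call for a judgement at the bedside, which needs no coding scale. They show only that the protocol expects component-level judgements to be possible.

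Fifth, the case report form is not in the documents and may already hold an SBRT field. It may, but the protocol requires only the drug field.

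Lastly, attribution does not cure low precision, and in an open-label trial it is subjective. That limits what the added tables can show. It does not justify tables whose definition and data disagree.

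**Conclusion.** The point holds in a limited form. Under the stated rules an SBRT-only event is coded unrelated to study drug and drops out of the related events in that summary. The broader treatment-related definition in 12.2.2 has no required field behind it, and Appendix 6 cannot supply one because it merges agent and procedure. Events are still captured and compared by arm, so the overall safety comparison survives, with half-widths of about 13 to 21 points under the assumed rates.

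The number of events misplaced cannot be estimated, because the documents give no rate of SBRT toxicity in this setting. The conclusion assumes that investigators apply 9.1.5 literally and that the form holds no field beyond what the protocol requires. It is best classed as a cheap improvement.

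**What to change.** - In Sections 9.1.5 and 9.2 and in Appendix 6, record relatedness to apalutamide and to SBRT as two separate judgements on one common scale, and say where a doubtful relationship falls. Keep the drug-specific judgement for IND and manufacturer reporting.
- In Section 12.2.2, use one term. Define treatment-related as at least possibly related to either component, and tabulate apalutamide-related, SBRT-related and either by arm, next to the all-cause table.
- Restate the missing-relationship rule for each field, with the SBRT field not applicable in Arm A, so that a blank there is not counted as related.

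The cost is one extra field on the adverse event form and a wording amendment. No treatment rule or sample size changes. There are two drawbacks to report with the tables. SBRT attribution is unblinded and can arise only in Arm B, so it describes that arm and is not a between-arm comparison. Any re-attribution of events already recorded would be retrospective and must be flagged as such.

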9.1.6 Severity

Signs or symptoms should be graded and recorded by the Investigator according to the National Cancer Institute’s Common Terminology Criteria for Adverse Events (CTCAE) Version 4.03 ([Appendix 4](#)). When specific adverse events are not listed in the CTCAE, they are to be graded as mild, moderate, severe, or life-threatening according to the following grades and definitions:

Table 2 AE Severity Grading

Severity (Toxicity Grade)	Description
Grade 1	Mild; asymptomatic or mild symptoms; clinical or diagnostic observations only; intervention not indicated
Grade 2	Moderate; minimal, local or noninvasive intervention indicated; limiting age- appropriate instrumental activities of daily living (ADL)
Grade 3	Severe or medically significant but not immediately life-threatening; hospitalization or prolongation of hospitalization indicated; disabling; limiting self-care ADL
Grade 4	Life-threatening consequences; urgent intervention indicated
Grade 5	Death related to AE

9.1.7 Individual Case Safety Report (ICSR)

A valid ICSR must contain the four minimum criteria required to meet regulatory reporting requirements.

1. an identifiable subject (but not disclosing personal information such as the subject's name, initials or address)
2. an identifiable reporter (investigational site)
3. a Janssen medicinal product
4. an adverse event, outcome, or certain special situations

The minimum information required is:

1. suspected Janssen medicinal product (doses, indication)
2. date of therapy (start and end date, if available)
3. batch or lot number, if available
4. subject details (subject ID and country)
5. gender
6. age at AE onset
7. reporter ID
8. adverse event detail (AE verbatim in English), onset date, relatedness, causality, action taken, outcome, (if available)
9. protocol ID

9.1.8 Special Reporting Situations

Safety events of interest for a Janssen medicinal product that require expediting reporting and/or safety evaluation include, but are not limited to:

- Drug exposure during pregnancy (maternal and paternal)
- Overdose of a Janssen medicinal product
- Exposure to a Janssen medicinal product from breastfeeding
- Suspected abuse/misuse of a Janssen medicinal product
- Inadvertent or accidental exposure to a Janssen medicinal product
- Medication error involving a Janssen medicinal product (with or without patient exposure to the Janssen medicinal product, e.g., name confusion)
- Suspected transmission of any infectious agent via administration of a medicinal product

These safety events may not meet the definition of an adverse event; however, from Janssen Scientific Affairs perspective, they are treated in the same manner as adverse events. Special situations should be recorded on the Adverse Event page of the CRF.

Any special situation that meets the criteria of a serious adverse event should be recorded on a Serious Adverse Event Report Form and be reported to the Sponsor-Investigator, who will then report the event to Janssen Scientific Affairs within 24 hours of becoming aware of the event.

9.1.9 Pregnancy

Because the Janssen medicinal product may have an effect on sperm, pregnancies in partners of male subjects exposed to a Janssen medicinal product will be reported by the Principal Investigator within 24 hours of their knowledge of the event using the Serious Adverse Event Form."

Follow-up information regarding the outcome of the pregnancy and any postnatal sequelae in the infant will be required.

9.2 ADVERSE EVENTS MONITORING

All adverse events, whether or not unexpected, and whether or not considered to be associated with the use of the study drug, will be entered into OnCore®, as noted above.

The Investigator will assess all adverse events and determine reportability requirements to the UCSF Data and Safety Monitoring Committee (DSMC) and UCSF's Institutional Review Board (IRB); and, when the study is conducted under an Investigational New Drug Application (IND), to the Food and Drug Administration (FDA) if it meets the FDA reporting criteria.

All adverse events entered into OnCore® will be reviewed by the Helen Diller Family Comprehensive Cancer Center Site Committee on a weekly basis. The Site Committee will review and discuss at each weekly meeting the selected toxicity, the toxicity grade, and the attribution of relationship of the adverse event to the administration of the study drug(s).

All grade(s) 3-5 adverse events entered into OnCore® will be reviewed on a monthly basis at the Site Committee meetings. The Site Committee will review and discuss the selected toxicity, the toxicity grade, and the attribution of relationship of the adverse event to the administration of the study drug(s).

In addition, all suspected adverse reactions considered "serious" entered into OnCore®, will be reviewed and monitored by the Data and Safety Monitoring Committee on an ongoing basis and discussed at DSMC meetings, which take place every six weeks.

For a detailed description of the Data and Safety Monitoring Plan for a Multicenter Phase 2 or 3 Institutional Study at the Helen Diller Comprehensive Cancer Center please refer to Appendix 6 Multicenter Institutional Studies.

9.3 REPORTING REQUIREMENTS

All AEs and SAEs whether reported by the patient, discovered during questioning, directly observed, or detected by physical examination, laboratory test or other means, will be recorded in the patient's medical record and on the appropriate study-specific CRFs.

Analyses will be performed for all patients having received at least one dose of study drug. The study will use the CTCAE v4.03 for reporting of non-hematologic adverse events and modified criteria for hematologic adverse events, see Appendix 4.

The Sponsor-Investigator at the UCSF Coordinating Center will hold the role of Study Chair ([name]). The Study Chair is responsible for the overall conduct of the study and for monitoring its safety and progress at all participating sites.

Anticipated events will be recorded and reported as described in Section 9.3.3.

9.3.1 SAE Reporting to the Sponsor-Investigator and Janssen

All participating sites will report SAEs to the Sponsor-Investigator within 24 hours of knowledge of the event. The Sponsor-Investigator will report to Janssen within 24 hours of being notified of the event, using MedWatch forms, as outlined below:

Procedures for Reporting Safety Data and Product Quality Complaints (PQCs) for Janssen Medicinal Products to Janssen

All adverse events and special situations, whether serious or non-serious, related or not related, following exposure to a Janssen medicinal product are to be documented by the investigator and recorded in the CRF and in the subject's source records. Investigators must record in the CRF their opinion concerning the relationship of the adverse event to a Janssen medicinal product.

All (serious and non-serious) adverse events reported for a Janssen medicinal product should be followed-up in accordance with clinical practice.

SAEs and Special Reporting Situations

All serious adverse events that have not resolved by the end of the study, or that have not resolved upon discontinuation of the subject's participation in the study, must be followed until any of the following occurs:

- The event resolves
- The event stabilizes
- The event returns to baseline, if a baseline value/status is available
- The event can be attributed to agents other than the study drug or to factors unrelated to study conduct
- It becomes unlikely that any additional information can be obtained (subject or health care practitioner refusal to provide additional information, lost to follow-up after demonstration of due diligence with follow-up efforts)

All participating sites will report all SAEs and special situations following exposure to a Janssen product under study to the Sponsor-Investigator within 24 hours of knowledge of the event, using MedWatch forms. UCSF and the Sponsor-Investigator will transmit all SAEs and special situations following exposure to a Janssen product under study using MedWatch form within 24-hours of becoming aware of the event(s).

All follow-up information for serious adverse events that are not resolved at the end of the study or by the time of patient withdrawal must be reported by participating sites to the Sponsor-Investigator within 24 hours of knowledge of the event. SAE follow-up information will be reported directly to Janssen by the Sponsor-Investigator, within 24 hours becoming aware, using the MedWatch form. The Sponsor-Investigator will also notify the UCSF DSMC of any SAEs.

Reporting Deaths: Regardless of relationship to study drug, all deaths on study should be reported to Janssen through and including 30 days after the last dose of study. Deaths occurring after the safety follow-up period do not have to be reported as SAEs unless considered related to study drug. All study drug related deaths should be reported to the UCSF DSMC within 1 business day of becoming aware. All deaths will be reviewed by the UCSF DSMC.

All available clinical information relevant to the evaluation of a related SAE or special situation is required.

- For all SAEs, the Investigator is obligated to pursue and provide information to the Sponsor-Investigator and Janssen in accordance with the timeframes for reporting specified above. In addition, an Investigator may be requested to obtain specific additional follow-up information in an expedited fashion. This information may be more detailed than that captured on the AE CRF. In general, this will include a description of the adverse event in sufficient detail to allow for a complete medical assessment of the case and independent determination of possible causality.
- Information on other possible causes of the event, such as concomitant medications and illnesses must be provided. In the case of a patient death, a summary of available autopsy findings must be submitted as soon as possible to the Sponsor-Investigator or designated representative and Janssen.
- UCSF and the Sponsor-Investigator is responsible for ensuring that these cases are complete and if not are promptly followed-up. A safety report is not considered complete until all clinical details needed to interpret the case are received. Reporting of follow-up information should follow the same timeline as initial reports.

All events should be followed to their resolution, until the Investigator assesses them as stable, irreversible, or until the patient is lost to follow-up, whichever comes first. Any SAEs occurring any time after the reporting period must be promptly reported if a causal relationship to apalutamide is suspected.

Copies of SAE Reporting to Regulatory Authorities to Janssen within 24 hours:

Copies of any and all relevant correspondences with regulatory authorities and ethics committees regarding any and all serious adverse events, irrespective of association with the Janssen Product under study, **are to be provided to Janssen within 24 hours of such report or correspondence being sent to applicable regulatory authorities.**

Product Quality Complaint (PQC) Handling:

A product quality compliant is defined as any suspicion of a product defect related to a potential quality issue during manufacturing, packaging, release testing, stability monitoring, dose preparation, storage or distribution of the product, or delivery system. Not all PQCs involve a subject. Lot and batch numbers are of high significance and need to be collected whenever available.

Examples of PQC include but not limited to:

- Functional Problem: e.g., altered delivery rate in a controlled release product
- Physical Defect: e.g. abnormal odor, broken or crushed tablets/capsules
- Potential Dosing Device Malfunction: e.g., autoinjector button not working, needle detaching from syringe
- Suspected Contamination
- Suspected Counterfeit

PQC Reporting:

A PQC may have an impact on the safety and efficacy of the product. Timely, accurate, and complete reporting and analysis of PQC information from studies are crucial for the protection of patients, investigators, and Janssen, and are mandated by regulatory agencies worldwide. Janssen has established procedures in conformity with regulatory requirements worldwide to ensure appropriate reporting of PQC information. Lot and/or Batch #s shall be

collected or any reports failure of expected pharmacological action (i.e., lack of effect). The product should be quarantined immediately and if possible, take a picture.

All initial PQCs involving a Janssen medicinal product under study must be reported by participating sites to the Sponsor-Investigator **within 24 hours of knowledge of the event**. The Sponsor-Investigator will report all initial PQCs to Janssen **within 24 hours after being made aware of the event**. The Janssen contact will provide additional information/form to be completed.

If the defect for a Janssen medicinal product under study is combined with either a serious adverse event or non-serious adverse event, the Sponsor-Investigator must report the PQC to Janssen and the UCSF coordinating center according to the serious adverse event reporting timelines. A sample of the suspected product should be maintained for further investigation if requested by Janssen.

Transmission Methods:

The following methods are acceptable for transmission of safety information to Janssen:

- Electronically via Janssen SECURE Email service (preferred)
- For business continuity purposes, if SECURE Email is non-functional:
 - Facsimile (fax), receipt of which is evidenced in a successful fax transmission report
- Telephone (if fax is non-functional).

Reporting Procedures for Reporting Safety Data and Product Quality Complaints (PQCs) for Non-Janssen Medicinal Products

For SAEs, special reporting situations and PQCs following exposure to a non-Janssen medicinal product under study, the site should notify the UCSF coordinating center, and the UCSF Sponsor-Investigator should notify the appropriate regulatory/competent authority or the manufacturer of that medicinal product (in the absence of appropriate local legislation) as soon as possible.

